1.1 Power Analysis

We performed a sample size analysis to determine the appropriate number of subjects to enroll in order to assure that we would achieve adequate statistical power. For an alpha level of .05, and an anticipated effect of 0.5 (medium), and a power of .8, we need a total of 102 (50 in each rehabilitation group) for a one-tailed (Strategic Advantage > Informational Advantage) directional hypothesis. Based on these analyses we plan to enroll 100 participants. These individuals will be randomized into the two intervention arms.

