1.2 Statistics for Primary Outcome Measures

Virtual Multiple Errands Test (VMET): We will evaluate intervention efficacy by comparing the performance of the VR-EFT group to that of the VR-BHT group on performance-based measures of executive function ability related to daily life. This first test will evaluate near-transfer of intervention skills to the VMET, a test of executive functions evaluated in a computerized format. VMET requires working memory, planning, coordinating, and prioritizing, thus it serves as a global, performance-based measure of executive function. We will evaluate change on total number of errors from the pre-intervention baseline using a 2 (group) x 2 (testing session) repeated-measures ANOVA followed by Bonferroni-correct post-hoc tests to evaluate the significance of simple mean comparisons. We predict a significant time-by-group interaction in which the VR-EFT group will perform more accurately relative to the VR-BHT group at the post-intervention test, but not at the pre-intervention test. In the event that this measure proves insensitive, we will compute and analyze sub-scores based on strategy errors, completion errors, and rule-violation errors applying an additional Bonferroni multiple comparison correction for the use of three sub-measures.

TBI Awareness Questionnaire: We will evaluate far-transfer to overall Awareness score, which is a reflection of actions carried out in a real life setting. Performance (averaged over sub-domains) will be evaluated using a 2 (group) x 2 (testing session) repeated-measures ANOVA, followed by post-hoc tests corrected for multiple comparisons. We predict a time-by-group interaction with superior life outcomes reported by the Strategic Advantage group over the Informational Advantage group at the post-intervention time point only with no reliable differences expected at the pre-intervention phase.

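### Section 1.2 attaches no gate, alpha split or success rule to its two primary outcomes, and its VMET sub-score fallback does not count the total-score test already made

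*SAP*

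**What the plan says.** SAP section 1.2 covers the primary outcome measures and describes two. The VMET total error count comes first: "This first test will evaluate near-transfer of intervention skills to the VMET". Its hypothesis is an interaction: "We predict a significant time-by-group interaction in which the VR-EFT group will perform more accurately". The Awareness questionnaire follows: "We will evaluate far-transfer to overall Awareness score", with its own hypothesis: "We predict a time-by-group interaction with superior life outcomes reported by the Strategic Advantage group". Each outcome has a 2 x 2 repeated-measures ANOVA, with corrected post-hoc comparisons inside that outcome.

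For the VMET there is a second route: "In the event that this measure proves insensitive, we will compute and analyze sub-scores". The sub-scores are strategy, completion and rule-violation errors, and they are analysed "applying an additional Bonferroni multiple comparison correction for the use of three sub-measures".

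The only significance level and the only sidedness are in section 1.1, in the power calculation: "For an alpha level of .05", for a "one-tailed (Strategic Advantage > Informational Advantage) directional hypothesis". Section 1.2 gives neither for the ANOVA tests.

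**The concern.** Two gaps sit in one section.

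- **Across the two primaries.** Both carry a prediction, and nothing says what happens when they disagree. The VMET is called the first test, so an order of presentation exists, but no consequence follows from it. A reader of the results could not tell from the SAP whether a significant Awareness result after a failed VMET is a primary success.
- **Inside the VMET.** The fallback is a written rule, so this is not a matter left to the protocol. Insensitivity is not defined. If a non-significant total counts as insensitive, the VMET question is asked again in three parts at alpha/3 each, after the total has already used the full alpha. Bonferroni for three tests limits error among the sub-scores, not over the total and the sub-scores together.

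At stake is how a positive primary claim may be reached, and whether its error rate is the .05 on which the trial was sized.

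**Working it through.** **Inputs from SAP section 1.1:** alpha .05, one-tailed, effect 0.5, power .8, 102 needed, 100 planned (50 per arm). **From section 1.2:** two primary interaction tests; three sub-scores with a Bonferroni factor of three. **Assumed, because the SAP gives none of it:** the correlations; that the total is the sum of three equal-variance sub-scores with a common correlation; and that 0.5 is the standardised group difference tested by the interaction.

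**1. The plan's own sample size.** Exact noncentral t, one-tailed .05, effect 0.5: 51 per arm gives 80.6% power, so 2 x 51 = 102, as stated. With 50 per arm (df 98, noncentrality 0.5 x sqrt(50/2) = 2.5) power is 79.9%. The sizing is for a single test at the full one-tailed .05.

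**2. Two primaries, no fallback, no true effect.**
- Either suffices, one-tailed .05: 1 - 0.95^2 = 9.75% if independent; 8.8% at correlation 0.5; bound .05 + .05 = 10%.
- Either suffices, two-sided .05, counting results that favour the intervention: 1 - 0.975^2 = 4.9%; 4.5% at correlation 0.5; bound 5%.
- Both must succeed, one-tailed: 0.05^2 = 0.25%; 1.2% at correlation 0.5.

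**3. VMET fallback, opened whenever the total is not significant** (null simulation, at least 2,000,000 draws). A false VMET result is a total significant at alpha, or any sub-score significant at alpha/3.

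| Sub-score correlation | One-tailed .05 | Two-sided .05, favouring the intervention (nominal .025) |
|---|---|---|
| 0 | 8.0% | 4.2% |
| 0.3 | 7.0% | 3.7% |
| 0.8 | 5.3% | 2.7% |
| Bound | .05 + 3 x .05/3 = 10% | .025 + 3 x .025/3 = 5% |

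One-tailed, the rate is 6.4% at correlation 0.5 and 5.7% at 0.7.

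**4. Fallback plus Awareness, either outcome sufficing.** One-tailed: 12.6% with all correlations 0, and 10.0% with the sub-score correlation and the correlation between outcomes both at 0.5 (bound 15%). Two-sided, favouring the intervention: 6.6% and 5.3% for the same two cases (bound 7.5%). Higher correlations lower these further.

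**5. The same fallback, with the trigger judged without the group comparison and the sub-scores replacing the total.** One-tailed: 1 - (1 - .05/3)^3 = 4.9% if independent, bound 5%. Nothing is added.

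**6. All four VMET tests at alpha/4.** One-tailed error at .0125 each is 4.3% to 2.6% over sub-score correlations 0 to 0.8. Power for the VMET total at one-tailed .0125 with 50 per arm is 59.0%, against 79.9% at .05.

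**7. Fixed sequence, one-tailed .05, both effects 0.5.** VMET 79.9%. Confirmatory Awareness: 0.7989^2 = 63.8% if independent; about 66%, 69% and 71% at correlations 0.3, 0.5 and 0.7.

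**The case against.** The other side has five arguments.

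- **The ANOVA is non-directional.** A reader might infer from section 1.1 that the primary error rate is nearly double .05. That needs one-tailed tests and an either-suffices rule, and section 1.2 states neither. Under a two-sided .05 test, error favouring the intervention stays within 5% across the two primaries without the fallback. This stands, and the near-doubling can only be given conditionally. The unstated sidedness is a missing detail, not a contradiction.
- **A positive result may need the whole predicted pattern.** Section 1.2 predicts a group difference after the intervention and none before. Requiring a one-tailed interaction plus a corrected post-intervention difference gives about 0.5% to 0.9% error per outcome, and 1.1% to 1.9% for either of two independent outcomes (50 per arm, pre-post correlations 0.3 to 0.7 assumed, no fallback). But the SAP offers the pattern as a prediction and nowhere makes it the criterion for success.
- **Near and far transfer may be two separate claims.** If each is reported on its own, joint control is a choice. That is fair for the two-outcome part, but the fallback acts inside the VMET claim and is untouched.
- **Insensitive may mean a floor or ceiling effect.** A reader might infer that the fallback must inflate error. It need not, as step 5 shows. The SAP does not say which meaning applies, and that is the defect.
- **An order exists.** A reader might infer that the section sets none. It does call the VMET the first test; what is missing is a gate.

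**Conclusion.** The point holds in this form. Section 1.2 gives two primary tests an order of presentation but no gate, alpha split or success rule, and its fallback corrects for three sub-scores without counting the total.

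The fallback is the firmer half, because it does not depend on the rule across the two outcomes. If it opens on a non-significant total, VMET error exceeds its nominal level at every correlation examined, from marginally (correlation 0.8) to by more than half (correlation 0). The cross-outcome excess is conditional: it is large only if either outcome suffices and tests are one-tailed, and absent if both must succeed.

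The sizes rest on assumed correlations and on equal-variance sub-scores that sum to the total; only the bounds are free of those assumptions. The documents do not support saying that the trial's false-positive rate is 10% or more, only that the SAP as written does not rule it out. This should be fixed before results are seen. It does not invalidate the design.

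**What to change.** Add a short paragraph to section 1.2:

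1. VMET sub-score results are exploratory. They cannot count as a primary success and cannot open the test of Awareness.
2. The near-then-far order becomes a fixed sequence: VMET total at the full alpha, and Awareness confirmatory only if the VMET total is significant, otherwise exploratory.

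If the intent is that both outcomes must succeed, one sentence saying so replaces item 2, and no alpha split is needed.

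**Cost.** No added participants. VMET power is unchanged at 79.9% (one-tailed .05, 50 per arm, effect 0.5). Confirmatory Awareness power falls from 79.9% to about 64% to 71%, depending on the correlation between outcomes. If the interactions are tested two-sided at .05, VMET power is 69.7% and confirmatory Awareness 48.6% at independence (0.6969^2), about 55% at correlation 0.5. The sub-scores lose any confirmatory role.

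**If the sub-scores must stay confirmatory,** test the total and all three at alpha/4 each. That holds one-tailed VMET error at 2.6% to 4.3%, but power for the total falls to 59.0%. The gate to Awareness would then have to be restated, since the total would no longer carry the full alpha.

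### The switch from the VMET total to three sub-scores has no defined trigger, timing or status, and on one reading the total falls outside the multiplicity correction

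*SAP*

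**What the plan says.** SAP section 1.2, which covers the primary outcome measures, names the VMET measure first: "We will evaluate change on total number of errors from the pre-intervention baseline", analysed with a 2 x 2 repeated-measures ANOVA, "followed by Bonferroni-correct post-hoc tests to evaluate the significance of simple mean comparisons". It then gives the expected result: "We predict a significant time-by-group interaction in which the VR-EFT group will perform more accurately relative to the VR-BHT group" at post-test but not at pre-test. The next sentence is the contingency: "In the event that this measure proves insensitive, we will compute and analyze sub-scores" for strategy, completion and rule-violation errors, "applying an additional Bonferroni multiple comparison correction for the use of three sub-measures".

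Section 1.1 sets the error rate and power, "For an alpha level of .05, and an anticipated effect of 0.5 (medium), and a power of .8", and states that the sample size is "for a one-tailed (Strategic Advantage > Informational Advantage) directional hypothesis". Nothing else in the SAP returns to the sub-scores or to what would make the total insensitive.

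**The concern.** The contingency changes which VMET measure carries the result, and three things about it are left open: the criterion, whether it is judged before group differences are known, and the standing of the sub-scores afterwards. At least two readings fit the text.

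- **Reading (a), fallback.** The total is tested, is not significant, and is therefore called insensitive. The sub-scores are then tested. Four tests bear on VMET, but the added correction counts three.
- **Reading (b), replacement.** The total shows a floor or ceiling effect in pooled data blinded to group. The sub-scores replace it, and a factor of three is enough.

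Reading (a) cannot be dismissed, because the contingency directly follows the prediction of a significant interaction. Under it, a positive sub-score after a null total could be presented as primary evidence or rejected as exploratory. The SAP wording would support either side, and the question cannot be settled credibly once results are known.

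**Working it through.** **Inputs from SAP section 1.1:** alpha .05; standardised effect 0.5; power .8; one-tailed; 50 per arm. **From section 1.2:** total tested by the group-by-time interaction; sub-scores corrected for three. **Assumed, because the SAP does not give them:** the total is the sum of the three sub-scores; equal sub-score variances; a common correlation of 0 to .9 between sub-scores; normal data.

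**1. The plan's own sample size.** Normal approximation: n per arm = 2(1.645 + 0.842)² / 0.5² = 49.5, so 50 per arm and 100 in total. The noncentral t solution is 50.15, so 51 per arm and 102 in total. The planning figure reproduces. At 50 per arm the noncentrality is 0.5 × √25 = 2.5 on 98 df, and one-sided power at .05 is .799.

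**2. Upper limits under reading (a).** Total at .05 plus three sub-scores at .05/3 each:
- Sum of alphas: .05 + 3 × .0167 = .10.
- Four independent tests: 1 − .95 × (1 − .0167)³ = .097.

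These overstate the error, because a total is correlated with its own parts.

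**3. Simulation under the null.** 2,000,000 trials per setting (standard error at most .0002), 50 per arm, t-test on change, which is equivalent to the 2 x 2 interaction F test.

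| Rule | r = 0 | .3 | .5 | .7 | .8 | .9 |
|---|---|---|---|---|---|---|
| (a) total at .05 or any sub-score at .05/3, two-sided | .084 | .075 | .067 | .059 | .055 | .051 |
| (a) same, one-sided | .080 | .071 | .064 | .057 | .053 | .051 |
| (a) two-sided tests, only results favouring VR-EFT (total alone: .025) | .042 | .037 | .034 | .030 | .028 | .026 |
| (a) sub-scores at .05/6, two-sided | .066 | .060 | .056 | .052 | .051 | .050 |
| (b) sub-scores at .05/3 replace the total, two-sided | .049 | .048 | .045 | .039 | .036 | .030 |

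The .05/6 row takes the word *additional* to mean that the factor of three is stacked on a correction for two post-hoc comparisons. With sub-score SDs of 3:1:1 (1,000,000 trials), the first row becomes .082 at r = 0 and .052 at r = .9.

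**4. A stricter success rule.** Suppose a claim needs both the interaction and a post-test comparison corrected for two, with pre-post correlation .5. The SAP does not state this rule. The false-positive rate with the fallback is then .0043 at r = 0, falling to .0028 at r = .9, against about .0028 for the total alone.

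**5. Power if all four tests shared alpha.** At .05/4 = .0125, one-sided power for the total falls from .799 to .590.

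**The case against.** The strongest reply is that inflation arises only if insensitive means non-significant. The psychometric sense (floor, ceiling, little variation) is at least as natural for a measure, and there the plan is conservative. That stands as a limit on the size of the problem. It does not say which reading the SAP intends.

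Even under reading (a) the excess is modest. The .084 needs three uncorrelated components of a test the SAP treats as global; at correlations of .5 to .9 the range is .067 to .051. The hypothesis is directional, and false results favouring VR-EFT from the F test stay below .05. Both points are right, although that directional rate still exceeds the .025 that applies to the total alone.

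The stacked figures depend on an assumed factor of two. The post-hoc correction attaches to simple mean comparisons, and a 2 x 2 design has four simple effects. With a factor of four (.05/12) the two-sided error is .057 at r = 0 and .052 at r = .5, so little excess remains. The stacked figures are illustrations and not a property of the SAP.

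Finally, blinding procedures and VMET scoring may be in the protocol, which was not available. That weakens the missing blinding rule as a separate fault. It does not supply the trigger or the alpha accounting, which the SAP sets itself.

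**Conclusion.** The concern holds and should be fixed, with medium confidence. The trigger for the switch, its timing relative to group comparisons and the status of the sub-scores are all undefined for a primary outcome, and the stated correction leaves the total out. That follows from the text without any assumption.

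Type I error inflation is conditional. It arises under the fallback reading, where two-sided VMET error is .051 to .084 depending on a sub-score correlation the SAP does not give. It is smaller if the corrections are stacked and absent if the sub-scores replace the total after a blinded judgement. The figures rest on the total being the sum of the sub-scores and on the assumed variances and success rule. They show the possible size and do not measure it for this trial.

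**What to change.** Preferred: state that VMET total errors is the only VMET primary endpoint, tested at the full .05. Always report the three sub-scores as secondary at .05/3 each, confirmatory only if the total is significant and otherwise labelled exploratory.

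If the investigators want to keep the contingency, which serves their purpose when the total fails as a measure, define *insensitive* by a prespecified numerical floor or ceiling criterion. Require it to be judged on pooled data blinded to group before any group comparison, and state that the sub-scores then replace the total at .05/3 each.

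Either change is SAP wording only and costs no power for a test of the total. The downside of the first is the loss of a second route to a positive VMET claim. Testing the total and sub-scores as one family of four at .0125 is not recommended, because it cuts power for the total from about .80 to about .59.

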1.3 Secondary Outcome Measures

In addition to evaluation of near and far transfer of executive function training skills, we will evaluate a series of subcomponents that are expected to be actively improved by the intervention.

1.3.1 Performance on Neuropsychological Tests

The neuropsychological tests will be evaluated according to the procedures outlined for the use of the ANAM and the relevant scoring procedures for each additional test in the planned battery. These scores will be organized by primary domain and analyzed using 2 (group) x 2 (testing session) ANOVAs. The domains of interest for the neuropsychological battery are as follows: working memory, goal maintenance, verbal fluency and general cognition. These same groupings will be applied to the ANAM data as well with the exception of verbal fluency, as this domain is not examined in our ANAM battery.

Analysis of Game Performance Data Acquired During Intervention

Data from the Strategic Advantage and Informational Advantage weekly modules will be analyzed by total number of task errors and by completion times for each task in order to determine the degree of individual improvement on tasks from Day 1 to Day 5 during each of the four weeks. For the long term memory module we will also analyze total recall scores across the week. We will apply this same analysis to the overall recall scores obtained in Week 4 during the composite game-based simulation.
